6.1 Primary Endpoint

The primary outcome measures are the American Orthopaedic Foot and Ankle Society (AOFAS) Ankle-Hindfoot Scale score and the SF-36 Health Survey Score as it pertains to the patient's ankle/foot. These assessments will be given to the patient in the pre-operative and post-operative periods.

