6.4 Statistical Methods

6.4.1 Analysis of Primary Outcome of Interest

All analysis will begin with assessment of the normality of continuous variables using the Kolmogorov-Smirnov test. Normally distributed continuous variables will be reported as means and standard deviations; non-normally distributed data as median and interguartile range. Categorical data will be reported as counts and percentages. The Student's t-test will be used to compare continuous demographic and clinical data between the immediate weight-bearing and non-weight-bearing groups. The chi-square test or Fisher's exact test will be used to compare categorical data between groups. Cronbach's alpha will be used to measure reliability, or internal consistency, of both the Medical Outcomes Study 36-Item Short Form Health Survey (SF-36) and the AOFAS Ankle-Hindfoot Scale survey (AOFAS). Spearman's rank correlation coefficient will be used to assess the relationship between the physical and mental component scores and the eight subdomain scores from the SF-36 and the pain, function and alignment scores of the AOFAS. SF-36 scores and AOFAS scores will be adjusted for patient age, gender, BMI and presence of diabetes mellitus. Nonparametric tests will be used when data breaks the normality assumption. A value of p<.05 on twotailed testing will be considered statistically significant. Statistical analysis will be performed using IBM-SPSS Statistics, version 24.0 (IBM-SPSS Inc., Armonk, NY). Using one-way repeated measures analysis of variance (ANOVA), differences over time in radiographic and advanced imaging parameters will be assessed separately for the immediate weight-bearing and non-weight-bearing groups. Two-way repeated measures ANOVA will be used to assess differences over time in these parameters between the two groups. Tukey's test or Dunn's procedure will be used for post-hoc pairwise comparisons, as indicated.

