Descriptive statistics on the physical and mental component scores and the eight subdomain scores from the SF-36 will be reported for the immediate weight-bearing and non-weight bearing groups. In order to examine differences in SF-36 scores within each group over time, a one-way repeated measures ANOVA will be conducted to determine if the SF-36 scores are significantly different between visits (e.g., screening, post-operative at 6-8 weeks, post-operative at 12 months, and post- operative at 24 months). A two-way repeated measures ANOVA will be conducted to determine if the SF-36 scores are significantly be conducted to determine if the SF-36 scores are significantly be conducted to determine if the SF-36 scores are significantly be conducted to determine if the SF-36 scores are significantly be conducted to determine if the SF-36 scores are significantly be conducted to determine if the SF-36 scores are significantly be conducted to determine if the SF-36 scores are significantly be conducted to determine if the SF-36 scores are significantly different between the two groups for these same visits. Post-hoc pairwise comparisons using Tukey's test or Dunn's procedure will be performed, as indicated.

Descriptive statistics on the pain, function and alignment component scores from the AOFAS will be reported for the immediate weight-bearing and non-weight bearing groups. In order to examine differences in AOFAS scores within each group over time, a one-way repeated measures ANOVA will be conducted to determine if the AOFAS scores are significantly different between visits (e.g., screening, post-operative at 6 – 8 weeks, post-operative at 12 months, and post-operative at 24 months). A two-way repeated measures ANOVA will be conducted to determine if the AOFAS scores are significantly different between visits. Post-hoc pairwise comparisons using Tukey's test or Dunn's procedure will be performed, as indicated.

The chi-square test will be used to examine the frequency of complications during the perioperative and post-operative periods, osseous healing as assessed by both clinical and radiographic evaluation and frequency of soft tissue procedures between the immediate weight-bearing and non-weight bearing groups.

Logistic regression analysis will be performed to assess which patient characteristics and surgical characteristics are associated with higher SF-36 scores and AOFAS scores.

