Due to the potential small sample sizes associated with the various orthopaedic procedures included in this study, the primary analysis will focus on the comparison of the immediate weight-bearing and non-weight bearing groups. Any analyses associated with an individual orthopaedic procedure will be considered exploratory. Finally, the data will not be adjusted for the center where the procedure was performed.

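### The AOFAS two-way ANOVA is stated as a test between visits and names no arm contrast, model term or primary visit, unlike the SF-36 and imaging sentences

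*Combined protocol and SAP*

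**What the plan says.** Section 6.1 names two primary outcomes: "The primary outcome measures are the American Orthopaedic Foot and Ankle Society (AOFAS) Ankle-Hindfoot Scale score and the SF-36 Health Survey Score".

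Section 6.4.1 gives AOFAS two repeated measures analyses:

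- Within each arm: "In order to examine differences in AOFAS scores within each group over time, a one-way repeated measures ANOVA will be conducted", to see whether scores differ between visits.
- Then the two-way analysis: "A two-way repeated measures ANOVA will be conducted to determine if the AOFAS scores are significantly different between visits".

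The same section words the two parallel analyses differently. For SF-36, the two-way ANOVA asks whether scores are "significantly different between the two groups for these same visits". For imaging: "Two-way repeated measures ANOVA will be used to assess differences over time in these parameters between the two groups".

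The visits given as examples for both questionnaires are screening, 6–8 weeks, 12 months and 24 months. Section 6.4.1 also says the SF-36 and AOFAS scores will be adjusted for age, gender, BMI and diabetes, without naming the model. It closes by saying that "the primary analysis will focus on the comparison of the immediate weight-bearing and non-weight bearing groups".

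Section 6.5 bases the sample size on an independent-samples t-test between arms on both questionnaires: d = 0.40, two-sided 0.05, 100 evaluable per arm, 80% power. No visit is named for that test.

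**The concern.** As worded, the AOFAS two-way ANOVA asks what the one-way ANOVA already asks within each arm: do scores change over time? Scores can change after surgery in both arms whatever the weight-bearing regimen, so a significant visit effect would not answer the trial's question.

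Nothing else in 6.4.1 fills the gap. The Student's t-test is for demographic and clinical data, with no questionnaire or visit named. The logistic regression concerns which characteristics go with higher scores. An analyst could therefore report a group main effect, a group-by-visit interaction, a test at one visit or a set of post-hoc pairs, and could choose after seeing the data. These options test different hypotheses and have different power.

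Screening adds a second ambiguity, which SF-36 shares. It is listed among the visits. If it is also an outcome visit in the two-way model, a group main effect averages in a pre-surgery score on which no arm effect is expected.

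**Working it through.** **1. The wording side by side (all section 6.4.1)**

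| Outcome | Question put to the two-way ANOVA | Arms named? |
|---|---|---|
| Imaging | differences over time between the two groups | yes |
| SF-36 | difference between the two groups at the listed visits | yes |
| AOFAS | difference between visits | no |

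**2. The plan's own figure**

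Inputs from 6.5: d = 0.40 (SD = 1 on the standardised scale), n = 100 per arm, two-sided alpha 0.05.

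- Noncentrality = d × √(n/2) = 0.40 × √50 = 2.83.
- Power, normal approximation = Φ(2.83 − 1.96) = 80.7%. The exact t-test gives 80.4%.
- Size needed for 80% power: 99 per arm by the normal formula. The exact t calculation gives 99.08, so 100 per arm.
- With the 15 per arm added for loss to follow-up: 115 per arm, 230 in total.

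The stated figures reproduce. They hold for one comparison of arm means.

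**3. A group main effect with screening as an outcome visit**

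Assumptions, none of them given in the documents: the arm difference is 0.40 SD at every post-operative visit and zero at screening; the SD is the same at all visits; any two visits have the same correlation ρ, taken as 0.3 to 0.7.

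- Mean arm difference over the four listed visits = (0 + 0.40 + 0.40 + 0.40)/4 = 0.30.
- Variance of a patient's mean over k visits = [1 + (k − 1)ρ]/k.
- Power = Φ(difference/√variance × √50 − 1.96).

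| Visits averaged | ρ | Difference | Variance | Noncentrality | Power |
|---|---|---|---|---|---|
| Screening + 3 post-operative | 0.3 | 0.30 | 0.475 | 3.08 | 87% |
| Screening + 3 post-operative | 0.7 | 0.30 | 0.775 | 2.41 | 67% |
| 3 post-operative only | 0.3 | 0.40 | 0.533 | 3.87 | 97% |
| 3 post-operative only | 0.7 | 0.40 | 0.800 | 3.16 | 89% |

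Including screening costs about 10 percentage points at ρ = 0.3 and about 21 at ρ = 0.7 (88.5% − 67.4%). Power with screening included falls below 80% once ρ exceeds about 0.43. This follows from setting 0.30 × √50/√variance = 1.96 + 0.84, which gives variance 0.573 and ρ = (4 × 0.573 − 1)/3.

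**4. Sensitivity to the visit list**

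The four visits are only examples. The schedule of procedures has five questionnaire visits, including 3 months, and section 7.5 also says five. With all five, the averaged difference is 4 × 0.40/5 = 0.32. The same formulas give about 93% to 74% with screening, against about 98% to 89% for the four post-operative visits. The pattern is unchanged.

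**The case against.** The best defence is that this is a drafting omission. A two-way ANOVA needs a second factor. It follows a one-way ANOVA run within each group, and group is the only second factor the plan uses elsewhere. The closing statement of 6.4.1 commits the primary analysis to the arm comparison, and 6.5 powers AOFAS on it. The SF-36 sentence in the same section contains a phrase repeated many times, so the text there may be damaged, and lost words in the AOFAS sentence cannot be excluded.

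Most of this stands, and it rules out three stronger readings:

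- **A reader might infer that AOFAS has no planned arm comparison.** The documents do not support that. Sections 6.4.1 and 6.5 both show the intent; what is missing is the contrast, the model term and the visit.
- **A reader might infer that arms will be compared by setting within-arm p-values side by side.** The plan never says so. It separates the within-group analysis from the two-way one.
- **A reader might infer a large power loss from Tukey comparisons over every arm-by-visit cell.** The text says only "Tukey's test or Dunn's procedure will be used for post-hoc pairwise comparisons, as indicated". It does not commit to that family of comparisons, and the same provision follows the correctly worded SF-36 analysis, so no such loss can be laid to the AOFAS sentence.

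Keeping screening as a visit and testing the group-by-visit interaction is also a recognised approach. The dilution in step 3 applies to a group main effect and not to that interaction. But the plan does not say which is meant, and showing that an arm comparison is intended does not settle which one is primary.

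**Conclusion.** The point holds as an inconsistency and an incomplete specification on a primary endpoint. The AOFAS sentence does not state the arm contrast that the SF-36 and imaging sentences state and that 6.5 powers.

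No stated figure is wrong: 100 evaluable and 115 enrolled per arm reproduce, and correcting the sentence leaves them unchanged. The power consequence is conditional. Under a group main effect that includes screening, power is about 87% to 67%, against about 97% to 89% for post-operative visits alone. This rests on a constant post-operative difference of 0.40 SD, equal variances and an assumed correlation of 0.3 to 0.7. At the low end of that range even the diluted contrast exceeds the planned 80%, so it would be wrong to say that the trial is necessarily underpowered. The screening issue applies equally to SF-36.

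The sentence should be corrected, preferably before any results by arm are examined.

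**What to change.** Use one specification for both AOFAS and SF-36, so that the two primary outcomes do not end up with different models:

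- Compare the arms in a repeated measures model on the post-operative visits with arm, visit and arm-by-visit terms. Include the screening score as a covariate, alongside the age, gender, BMI and diabetes adjustment already planned.
- Name one post-operative visit as the primary arm contrast, so that it matches the single t-test contrast powered in 6.5.
- Report the arm difference with a 95% confidence interval at each post-operative visit.
- Replace the example visit list with the definitive one, and say whether 3 months is included.
- Label the within-arm one-way ANOVAs descriptive.

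The cost is a small amount of rewording and analysis set-up. The questionnaires are already scheduled at screening and at the post-operative visits needed, so there is no added data collection and no change in sample size.

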5.1.3 Radiographic/Advanced Imaging

X-rays, CT, MRI, and/or ultrasound will be obtained, when indicated, at certain visits determined by the physician. These imaging modalities will evaluate bone healing, joint fusion, and soft tissue repair integrity.

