6.2 Secondary Endpoints

The secondary outcome measures are the frequency of complications during the perioperative and post-operative periods, osseous healing as assessed by both clinical and radiographic evaluation, and healing outcomes of soft tissue procedures. These results will be analyzed at the end of the follow-up period.

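### The chi-square sentence counts soft tissue operations by arm, so the secondary endpoint of soft tissue healing has no named analysis

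*Combined protocol and SAP*

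**What the plan says.** Section 6.2 names three secondary outcomes: complications, then "osseous healing as assessed by both clinical and radiographic evaluation, and healing outcomes of soft tissue procedures". It adds: "These results will be analyzed at the end of the follow-up period".

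The sentence in section 6.4.1 that assigns a test to these outcomes begins "The chi-square test will be used to examine the frequency of complications during the perioperative and post-operative periods, osseous healing as assessed by both clinical". Its last item is the "frequency of soft tissue procedures between the immediate weight-bearing and non-weight bearing groups".

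Other text that bears on the point:

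- Section 6.4.1 has a general rule: "The chi-square test or Fisher's exact test will be used to compare categorical data between groups". For imaging parameters it says: "Two-way repeated measures ANOVA will be used to assess differences over time in these parameters between the two groups".
- Section 5.1.3 says of imaging: "These imaging modalities will evaluate bone healing, joint fusion, and soft tissue repair integrity". The same section leaves it to the physician to decide when imaging is needed.
- The abstract (Study Interventions and Measures) has soft tissue procedures assessed clinically and by whatever imaging is thought suitable. No section says what counts as healed.
- Sections 7.1.2 and 7.4 say that taking part does not change the surgeon's decisions about the operation.
- Sections 6.8 and 7.3.2.6 list failed or slow soft tissue healing among the risks of immediate weight-bearing.

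**The concern.** The endpoint asks whether repaired soft tissue healed. The test asks how many soft tissue operations each arm had. The second quantity describes case mix and is no measure of the effect of weight-bearing.

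Two things are at stake. A risk that the protocol itself attributes to the study arm would have no stated between-arm comparison. And a difference in the types of operation between arms would be tested in the same sentence as complications and bone healing, where it could be reported as if it were a result of treatment.

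**Working it through.** **1. The two lists side by side.**

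| Item | Section 6.2 (endpoint) | Section 6.4.1 (chi-square test) | Match |
|---|---|---|---|
| 1 | Complications, perioperative and post-operative | Same | Yes |
| 2 | Bone healing, clinical and radiographic | Same | Yes |
| 3 | "healing outcomes of soft tissue procedures" | "frequency of soft tissue procedures between the immediate weight-bearing and non-weight bearing groups" | No |

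The order is the same and the first two items agree almost word for word. Only the third changes, from a healing result to a count of operations.

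**2. Can the count stand in for healing?** No. By sections 7.1.2 and 7.4 the operation is chosen without regard to participation. The count is the same whether every repair heals or none does. Reading the phrase as later, repeat operations does not fit either, because the abstract and section 6.2 use the term for the operation that brings the patient into the study.

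**3. Does another sentence supply the analysis?** Each candidate was checked for the outcome, the denominator and the time point.

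- General categorical rule (6.4.1): gives a test, but none of the three.
- Imaging ANOVA (6.4.1): covers imaging parameters over time. Imaging is obtained as needed, and clinical assessment of healing falls outside it.
- Complications test (6.4.1): may pick up some failures, but section 6.2 lists soft tissue healing separately from complications.
- Section 6.2: says when the analysis is done, but not how or in whom.

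**4. The cost of the right denominator.** The plan's only sample size figure (section 6.5) is for the questionnaires: d = 0.40, two-sided 0.05, 80% power. The normal approximation gives n = 2(1.960 + 0.842)²/0.40² = 98.1, so 99 per arm. The exact t calculation gives 99.08, so 100, with power 0.804 at 100 per arm. The figure reproduces. Adding 15 per arm gives 115, or 230 in total. It matters here only because the soft tissue subset can be no larger than the 100 evaluable patients per arm.

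The documents do not give the share of patients with a soft tissue procedure or any failure rate. The values below are assumptions, shown as a range.

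- Interval width: the half-width for a risk difference is 1.96·√[(p₁(1−p₁) + p₂(1−p₂))/n]. For the same rates, the ratio to n = 100 is √(100/n).
- Power: Φ{(|p₁−p₂| − 1.96·√[2p̄(1−p̄)/n]) / √[(p₁(1−p₁) + p₂(1−p₂))/n]}, where p̄ is the mean of the two rates.

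| Soft tissue patients per arm | CI width relative to 100 per arm | Power, 5% vs 15% failing | Power, 5% vs 20% failing |
|---|---|---|---|
| 25 | 2.0 | 21% | 36% |
| 50 | 1.41 | 38% | 62% |
| 75 | 1.15 | 53% | 80% |

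For example, with n = 50 and 5% vs 20%: (0.15 − 1.96 × 0.0661)/0.0644 = 0.316, and Φ(0.316) = 0.62.

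**The case against.** The strongest reply is that this is a slip of the pen. The parallel lists make it likely that healing was meant, and a sensible analyst would read it so. That is probably true, and it lowers the stakes. But the sentence is complete and grammatical, nothing elsewhere corrects it, and even a charitable reading leaves the criterion and the denominator open.

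A reader might go further and infer that soft tissue healing will not be analysed at all. The documents do not support that. The general chi-square or Fisher rule, the imaging ANOVA and the complications test could each reach part of it, and section 6.2 commits to analysing its outcomes at the end of follow-up. What stands is that none of them specifies this endpoint.

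A reader might also infer that the count test is harmless because it would reject only at its nominal level. That needs case mix to differ between arms by chance alone. Section 3.1 uses one coin flip and then alternates, and section 7.1.1 leaves recruitment to the surgeons' discretion. Table 1 places randomization at screening, before the operation. The plan intends the choice of operation to be independent of arm, but this design does not guarantee it, so no rejection rate can be stated.

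Nor does the list of procedure types on the data form show how large the soft tissue subset will be. It lists kinds of operation and gives no numbers of patients.

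**Conclusion.** The point holds in this form: the test named for the third secondary endpoint uses the wrong variable, and the endpoint has no named analysis. This follows from the text of sections 6.2 and 6.4.1 and needs no numerical assumption. The statement that the count carries no information on healing rests on sections 7.1.2 and 7.4, which separate the choice of operation from participation.

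The reach is limited to one of three secondary endpoints. It matters because poor soft tissue healing is a listed risk of the study arm. The correction should be made before the data are seen; an analysis chosen afterwards would be post hoc. The power and interval figures only illustrate the cost of the correction and are not estimates for this trial.

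**What to change.** In section 6.4.1, replace the procedure count with the section 6.2 outcome. Suggested content:

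- **Outcome:** the proportion of patients with failed or delayed soft tissue healing at the end of follow-up, by arm.
- **Denominator:** patients who had a soft tissue procedure. State that a patient with both soft tissue and bony procedures counts in each relevant subset, since the data form allows more than one procedure.
- **Test and estimate:** chi-square or Fisher's exact test, with the risk difference and its 95% CI.
- **Criterion:** pre-specify what counts as healed, delayed and failed, and which clinical and imaging findings decide it. Delay cannot be read from status at two years alone, so say which visits feed the classification.
- **Procedure counts by arm:** keep as baseline description only, without a place among the treatment results.

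The cost is a sentence of analysis text plus an outcome definition that the investigators must agree on. The comparison uses a subset, so its interval is wider than for the whole cohort and its power may be modest. The primary analysis and the sample size do not change.

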2.2 Secondary Objectives (or Aim)

The secondary objectives are to:

- Determine if there are specific procedures better suited to immediate weight-bearing.
- Determine if patient satisfaction is higher in an immediate weight-bearing group compared to NWB.
- Determine if immediate weight-bearing allows earlier return to work and/or sport.

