6.5 Sample Size and Power

The study power calculation is based on the primary endpoints.

Assuming the American Orthopaedic Foot and Ankle Society (AOFAS) Ankle-Hindfoot Scale score and the SF-36 Health Survey Score (as it pertains to the patient's foot/ankle) are normally distributed in the immediate weight-bearing and non-weight-bearing groups and using an independent-samples t-test with a .05 two-sided significance level, and (absent any prior study results) assuming a "medium" effect size of Cohen's d = 0.40, 200 evaluable patients (100 patients in each group) would give you a power of 80% to detect a true difference in means on the questionnaires, if present. Fifteen patients will be added to each group for the potential of loss to follow-up. Final sample size is 230 patients (115 patients in each group). Sample size was calculated using an a-priori sample size calculator for Student t-tests (2017) available from http://www.danielsoper.com.

¹ "Effect size" is a statistical expression of the magnitude of the difference between two groups (Portney and Watkins, 2000). The standardized mean effect, one type of effect size, expresses the mean difference between two groups in standard deviation units. This is

typically reported as Cohen's "d." Interpretation of effect size depends on the research question. Cohen (1988) defines his effect sizes as: 8 = large (8/10 of a standard deviation unit). 5 = moderate (1/2 of a standard deviation). 2 = small (1/5 of a standard deviation). I would recommend using the "medium" effect size for your project. A medium effect size can range from 0.3 to 0.5.

SAFETY MANAGEMENT

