MRI: Pre-Op: AOFAS: Follow-up Visit AOFAS: Follow-up Visit	VAS: #2 (6-8 weeks Post-Op): VAS: #4 (12 months Post-Op): VAS:	Procedure(s): 1 st MPJ fusion DMO 1 st TMT fusion LisFranc ORIF Midfoot fusion 5 th met ORIF TNJ fusion STJ fusion PCDO PMGL Achilles repair FHL transfer FDL transfer Peroneal repair ATT transfer PTT repair Fibula ORIF Tibia ORIF Bimal ORIF Ankle fusion TAR

TID#:		Date:	
	AOFAS Ankle-Hindfoot Scale (100	Points Total)	
1. Pain (40 points)			
	None	40	
	Mild, occasional	30	
	Moderate, daily Severe, almost always present	0	
2. Function (50 point	nts)		
Activity limitation	ns, support requirements		
No limitations, no su	t		10
No limitations, no su No limitations of dail	pport y activities, limitation of recreational a	ctivities no support	10
	ational activities, cane	curries, no support	4
	daily & recreational activities, walker, c	rutches, wheelchair, bra	
4-6 blocks 1-3 blocks			4 2
Less than 1 block			0
Walking surfaces			
No difficulty on any s	urface		5
Some difficulty on uneven terrain, stairs, inclines, ladders			
Severe difficulty on uneven terrain, stairs, inclines, ladders			
Gait abnormality	,		
None, slight			8
Obvious			4
Marked			0
5	flexion plus extension)		
Sagittal motion ()	ction (30° or more)		8
Normal or mild restri			
	(15° - 29°)		4

IRB#2018-XXXWPH: Immediate Weightbearing vs. Non-Weightbearing after Foot & Ankle Surgery: A Prospective Analysis

SF-36® Health Survey Scoring Demonstration

This survey asks for your views about your health as it pertains to your hindfoot fusion.

Answer every question by selecting the answer as indicated. If you are unsure about how to answer a question, please give the best answer you can.

1. In general, would you say your health is:

Excellent	Very good	Good	Fair	Poor
0	0	0	0	0

2. Compared to your pre-operative state, how would you rate your health in general now?

Much better	Somewhat better	About the same	Somewhat worse now	Much worse now
o	0	0	Ö	O

3. The following questions are about activities you might do during a typical day. Does your health now limit you in these activities? If so, how much?

		Yes, limited a lot	Yes, limited a little	No, not limited at all
а	Vigorous activities, such as running, lifting heavy objects, participating in strenuous sports	0	0	0
ь	Moderate activities, such as moving a table, pushing a vacuum cleaner, bowling, or playing golf	0	0	0
с	Lifting or carrying groceries	0	0	0

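### Logistic regression is planned for SF-36 and AOFAS scores, but no binary or ordinal outcome is defined, so the predictor analysis has no stated response variable

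*Combined protocol and SAP*

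**What the plan says.** The sentence at issue is in section 6.4.1 of the combined protocol and SAP: "Logistic regression analysis will be performed to assess which patient characteristics and surgical characteristics are associated with higher SF-36 scores and AOFAS scores". It does not say whether the model is binary or ordinal, what counts as a higher score, which visit is modelled, or which of the SF-36 and AOFAS scores is the response.

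The same scores appear elsewhere in these forms:

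- Section 6.5 assumes that they "are normally distributed in the immediate weight-bearing and non-weight-bearing groups" and powers the trial to "detect a true difference in means on the questionnaires".
- Section 6.4.1 plans repeated measures ANOVA, for example "a one-way repeated measures ANOVA will be conducted to determine if the AOFAS scores are significantly different between visits", and the same for SF-36.
- Section 6.4.1 also plans Spearman correlations between SF-36 and AOFAS scores, medians with interquartile ranges for non-normal data, and nonparametric tests where normality fails.
- The appendix form is headed "AOFAS Ankle-Hindfoot Scale (100 Points Total)", a points scale with no pass mark.

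Section 6.4.1 also says the scores will be adjusted for age, gender, BMI and diabetes, without naming a model. It closes by calling analyses of individual procedures exploratory. One secondary objective in section 2.2 reads "Determine if there are specific procedures better suited to immediate weight-bearing".

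**The concern.** The method does not match the variable. Ordinary logistic regression models the probability of an event, and the plan defines no event for a score that is "associated with higher SF-36 scores and AOFAS scores" in the wording of 6.4.1. Two things are at stake.

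The first is analytic freedom. Section 6.4.1 lists two component and eight subdomain scores for SF-36 and three component scores for AOFAS. Table 1 schedules the surveys at four post-operative visits (6-8 weeks, 3 months, 1 year and 2 years). That is (2 + 8 + 3) × 4 = 52 possible responses before any cut-point is chosen, judged at p<.05 with no multiplicity rule stated for this analysis.

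The second is efficiency. Cutting a continuous score in two discards information, so real predictors are more easily missed.

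This sentence is also the one place where the plan names a model linking surgical characteristics to the scores, which makes it a natural starting point for the secondary objective on procedures.

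**Working it through.** **Inputs.** From section 6.5: d = 0.40, 200 evaluable patients (100 per arm), normal scores, and a test "using an independent-samples t-test with a .05 two-sided significance level". Not in the documents, and so assumed: the cut-point (varied from the median to the 90th percentile) and the strength of a predictor (r = 0.15 to 0.25).

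**1. The plan's own figure.** For two means, n per arm = 2(1.96 + 0.842)²/0.40² = 98.1, so 99 by the normal approximation. The t-test needs 99.08, so 100. Power at 100 per arm is 80.4% by the t-test. Adding 15 gives 115 per arm, 230 in total. Section 6.5 reproduces, and it does not depend on the logistic sentence.

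**2. Can the sentence be run as written?** A binary logit fitted to raw 0-100 scores stopped with an error, because the response must lie between 0 and 1. An outcome has to be constructed first.

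**3. Information kept by a binary split.** For a normal score cut at quantile q, with c the matching normal deviate and φ the normal density, efficiency relative to the uncut score is φ(c)²/[q(1 − q)]. At the median this is 0.3989²/0.25 = 2/π = 0.637. The loss is 36.3%, and 200 patients act like 200 × 0.637 = 127.

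| Cut (percentile) | Efficiency | Loss |
|---|---|---|
| 50th | 0.637 | 36% |
| 60th | 0.622 | 38% |
| 67th | 0.595 | 40% |
| 75th | 0.539 | 46% |
| 80th | 0.490 | 51% |
| 90th | 0.342 | 66% |

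**4. Power for one normal predictor, 200 patients, two-sided .05.** Simulation, 4,000 data sets per r:

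| Assumed r | Linear | Logistic, median split |
|---|---|---|
| 0.15 | 57% | 39% |
| 0.20 | 81% | 61% |
| 0.25 | 95% | 81% |

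A Fisher-z check at r = 0.20 uses Φ(0.2027 × √(n − 3) − 1.96). With n = 200 this is Φ(0.885) = 81%. With n = 127 it is Φ(0.30) = 62%. The two methods agree.

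**5. Power for a two-group predictor of the size in section 6.5 (d = 0.40, 100 per group).** A median split gives proportions of 0.421 and 0.579. The two-proportion formula gives 61% power, with 155 per group needed for 80%. A simulation of this case gave 80% for the t-test and 67% for the median-split logit. The 67% is flattered by the coarse test. With both margins fixed at 100, the Wald test first rejects at a 57/43 split: 2 ln(57/43) = 0.564, standard error √[2(1/57 + 1/43)] = 0.286, z = 1.97. The null probability of a split that extreme in either direction is about 6.6%, not 5%.

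**6. The ordinal alternative.** A proportional-odds model uses the ordering of the scores. Its efficiency is close to the rank-based 3/π = 0.955, a loss of about 5%. In a simulation with scores in 10 ordered bands (600 runs per r), power for linear, ordinal and median-split models was 59%, 57% and 40% at r = 0.15; 82%, 81% and 61% at r = 0.20; and 95%, 94% and 81% at r = 0.25.

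**The case against.** The strongest reply is that the sentence says logistic regression, not binary logistic regression. An ordinal logistic model suits graded scores and costs almost nothing, as step 6 shows. The plan never proposes a median split. This stands against a reading a reader might be tempted to take: that the plan, as written, throws away a third of its information. The documents do not support that, because the 36% follows only if someone chooses a median split of normal scores. The reply does not remove the fault, since no ordinal model is named either and the response remains undefined.

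Other stronger readings also fail.

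- A reader might infer that section 6 otherwise treats the scores only as means. It does not: Spearman correlation, medians and nonparametric tests are planned too. What holds is that nowhere else in section 6 is a score made into a yes/no outcome.
- A reader might infer that this is the only analysis bearing on which procedures suit immediate weight-bearing. Section 6.4.1 anticipates exploratory analyses by procedure. As written, the logistic sentence names neither treatment arm nor an arm-by-procedure term, so it would not answer that objective under any model. That gap is separate from the choice of logistic or linear.
- The power figures use one normal predictor and assumed correlations. Many recorded characteristics (gender, diabetes, smoking status, about 20 procedures on the data form) are categorical, and the plan claims no power for this analysis. The figures illustrate the loss; they do not forecast this trial's power.

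**Conclusion.** The concern holds in limited form. The plan assigns logistic regression to scores for which it defines no binary or ordinal outcome, so the binary version cannot be run without an unplanned cut-point that could be chosen after seeing the data. Under normality, 36% is the smallest loss among the cuts examined, rising to 66% at the 90th percentile. Ceiling effects or the coarse AOFAS item scoring would change these figures.

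The fault is confined to a supporting predictor analysis. It would be wrong to infer that the primary between-arm comparison or the 230-patient sample size is undermined: both rest on means and ANOVA and do not use this model. It should be corrected because linear regression is a better method for these scores and is almost free to adopt.

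**What to change.** In section 6.4.1, replace logistic regression with multiple linear regression on the continuous SF-36 and AOFAS scores, or with a prespecified proportional-odds model if normality fails. Name the score or scores, the visit and the covariates; the four adjustment variables already listed in 6.4.1 are an obvious start.

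To inform the section 2.2 objective on procedures, include treatment arm, a prespecified grouping of procedures and their interaction, labelled exploratory in line with the end of 6.4.1. The documents define no such grouping, so it has to be written down before the data are examined.

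Nothing needs to change for complications or osseous healing, which the plan already assigns to the chi-square test.

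The cost is a short passage of SAP wording, some thought about grouping procedures, and a protocol modification to the IRB under section 6.6. No new data and no extra patients are needed.
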